9 MEDICAL HISTORY

Medical and surgical history data will be coded using Medical Dictionary for Regulatory Activities (MedDRA) version 20.0 or newer. The subject incidence will be summarized for each system organ class (SOC) and preferred term (PT). A subject will be counted only once per SOC or per PT for the summary.

A listing of the SOC, PT, body system, verbatim term for the medical history condition/event, start and stop dates (when available), and an indicator for whether or not the condition is ongoing at OL Baseline will be provided.

10 CONCOMITANT AND POST-TREATMENT MEDICATION

Medications will be coded using WHO Drug Dictionary (WHODRUG-DDE-B2) 2019 March or newer version. For concomitant medications, the number and percentage of subjects taking each drug class (ATC Level 3) and medication PT will be tabulated. A subject will be counted only once per drug class or per medication PT for the summary. Concomitant and post-treatment medications will be summarized separately.

10.1 Concomitant Medication

Concomitant medication is defined as any medication with a start date prior to the date of the OL first dose date and continuing after the OL first dose date, or with a start date between the OL first dose date and OL last dose date, inclusive.

10.2 Post-Treatment Medication

Post-treatment medication is defined as any medication with a start date after the OL last dose date.

10.3 COVID-19 Related Medications

Relationship to COVID-19 will be assessed by the investigator as detailed in the DMP Appendix B. Concomitant and post-treatment medication analyses described in [Section 10.1](#) and Section 10.2 above will also be summarized by relationship to COVID-19 (Not related to COVID-19 vs. Related to COVID-19).

11 EXTENT OF EXPOSURE AND TREATMENT COMPLIANCE

Summaries of exposure and compliance to OL study drug will be provided for the Safety Analysis Set.

11.1 Exposure to Study drug

Pimavanserin dose levels are expressed as free base.

For each subject the duration of exposure will be calculated as the number of days from first dose date to last dose date inclusive. See Sections 11.1.1 and 11.1.2 for further details.

11.1.1 Exposure to OL pimavanserin

Formulas to calculate subject level exposure-related quantities for OL pimavanserin are given as follows:

$$\text{Duration of OL exposure (days)} = \text{OL last dose date} - \text{OL first dose date} + 1$$

$$\text{Average OL daily dose (mg/day)} = \frac{\text{cumulative OL dose (mg)}}{\text{duration of OL pimavanserin exposure (days)}}$$

The total cumulative dose of pimavanserin will be calculated by first multiplying the number of tablets taken by the dose level (in mg) for each kit returned to the site during the OL study period and then summing the results for all kits.

If a subject has an unreturned kit then the overall cumulative dose and average daily dose will be set to missing

Duration of OL pimavanserin exposure will be summarized as both continuous and categorical variables. For the categorical presentation of duration of OL exposure the number and percentage of subjects in each of the following categories will be displayed: <2 weeks

(1 to 13 days), 2 to <4 weeks (14 to 27 days), 4 to <8 weeks (28 to 55 days), 8 to <12 weeks (56 to 83 days), 12 to <16 weeks (84 to 111), 16 to <28 weeks (112 to 195), 28 to <40 weeks (196 to 279), 40 to <52 weeks (280 to 363), and ≥ 52 weeks (≥ 364 days).

In addition, whether a subject had any dose changes (yes vs. no), and last dose level (20 mg vs. 34 mg) will be tabulated.

Kaplan-Meier curves of duration of exposure to OL pimavanserin will be provided.

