5 INVESTIGATIONAL PRODUCT

5.1 Investigational Product Description

The investigational product will be pimavanserin 20 mg (provided as 2×10 mg tablets) or pimavanserin 34 mg (provided as 2×17 mg tablets). Tablets will be administered orally as a single dose once daily.

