9.5.3 Other Safety Analyses

9.5.3.1 Exposure to Study Drug

For each subject, the duration of exposure to study drug in this study will be calculated as the number of days from first dose date to last dose date inclusive. A categorical summary will also be provided using categories defined in the SAP.

In addition, the maximum dose, final dose, and mean daily dose will be determined for each subject and summarized. For maximum dose and final dose, a categorical summary by dose level (20 mg and 34 mg) will be provided. For mean daily dose, summary statistics will be tabulated.

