11.1.2 Total exposure to double-blind and OL pimavanserin

For subjects who received pimavanserin in the antecedent study, formulas to calculate subject level total pimavanserin (DB+OL) exposure-related quantities are as follows:

$$\text{Total duration of exposure (days)} = (\text{OL last dose date} - \text{OL first dose date} + 1) + (\text{DB last dose date} - \text{DB first dose date} + 1)$$

$$\text{Total average daily dose (mg/day)} = \frac{\text{total cumulative dose (mg)}}{\text{total duration of exposure (days)}}$$

In case a subject whose last dose date in the antecedent study is equal to the first dose date in the OLE, the total duration of exposure will be the above calculation minus one.

The total cumulative dose of pimavanserin will be calculated by first multiplying the number of tablets taken by the dose level (in mg) for each kit returned to the site during both the DB and OL study periods and then summing the results for all kits.

For subjects who received placebo in the antecedent study, the pimavanserin total duration of exposure, total cumulative dose, and the average daily dose across the DB and OL periods will use the same values as calculated for the OL study alone (see Section 11.1.1).

Total duration of DB+OL exposure to pimavanserin will be summarized as both continuous and categorical variables. For the categorical presentation, the number and percentage of subjects in each of the following categories will be displayed: <2 weeks (1 to 13 days), 2 to <4 weeks (14 to 27 days), 4 to <8 weeks (28 to 55 days), 8 to <12 weeks (56 to 83 days), 12 to <16 weeks (84 to 111 days), 16 to <24 weeks (112 to 195 days), 28 to <40 weeks (196 to 279 days), 40 to <52 weeks (280 to 363 days), 52 to <60 (364 to 419 days), and ≥ 60 weeks (≥ 420 days).

In addition, summaries of whether subjects had any dose change (yes vs. no), their highest dose level (20 mg or 34 mg), and their last dose level (20 mg or 34 mg) will also be provided.

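### SAP 11.1.1 multiplies tablets taken by the two-tablet daily dose instead of the tablet strength, which doubles open-label dose as written; secondarily, the 11.2 compliance formula counts unreturned tablets as taken

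*SAP*

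**What the plan says.** **Dose.** SAP 11.1.1 obtains average daily dose by dividing cumulative dose by days of open-label exposure. Cumulative dose is "calculated by first multiplying the number of tablets taken by the dose level (in mg) for each kit returned to the site", then added up over kits. SAP 11.1.2 uses the same rule across the double-blind and open-label periods.

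The documents use *dose level* as follows:
- Protocol 9.5.3.1, for maximum and final dose: "a categorical summary by dose level (20 mg and 34 mg) will be provided"
- SAP 11.1.1: "last dose level (20 mg vs. 34 mg"
- SAP 11.1.2: "highest dose level (20 mg or 34 mg"

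Protocol 5.1 describes the product as "pimavanserin 20 mg (provided as 2×10 mg tablets) or pimavanserin 34 mg (provided as 2×17 mg tablets", taken once daily. Protocol 5.1.1 confirms that only 10 mg and 17 mg tablets are supplied, and its word for the amount per tablet is *strength*.

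On outputs, Protocol 9.5.3.1 states: "For mean daily dose, summary statistics will be tabulated". SAP 11 adds: "Summaries of exposure and compliance to OL study drug will be provided for the Safety Analysis Set".

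**Compliance.** SAP 11.2 takes open-label tablets dispensed minus tablets returned, divides by twice the days of exposure, and groups the percentage as below 80, 80 to 120, and above 120. It has no rule for drug that is lost or not returned. Two other places do address it. SAP 11.1.1 says: "If a subject has an unreturned kit then the overall cumulative dose and average daily dose will be set to missing". Protocol 5.1.6 says that, where drug can never be returned, compliance is determined from what the subject or caregiver reports.

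**The concern.** A tablet count has to be multiplied by milligrams per tablet. The SAP multiplies it by a quantity that, wherever the documents give it a value, is milligrams per day. Since a day's dose is two tablets, the stated rule counts each day's dose twice. Mean daily dose is a summary the protocol requires, in a study whose purpose is to describe long-term exposure.

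The compliance formula raises a different and smaller question. For a subject with an unreturned kit, 11.1.1 treats intake as unknown, while 11.2 still produces a percentage that assumes all of the missing tablets were swallowed. An under-complier who loses unused drug could then be shown in the middle category. Unlike a doubled dose, that value would not look odd.

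**Working it through.** **1. Reproduce the plan's daily doses.** Inputs are from Protocol 5.1: 2 × 10 = 20 mg and 2 × 17 = 34 mg. The factor of 2 in the SAP 11.2 denominator agrees with two tablets per day.

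**2. Apply the dose rule to a full complier over 52 weeks.** Exposure is 364 days, so tablets taken = 2 × 364 = 728.

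| Daily dose | Multiplier | Cumulative dose (mg) | Average (mg/day) |
|---|---|---|---|
| 34 mg | 34 (as written) | 728 × 34 = 24,752 | 68 |
| 34 mg | 17 (tablet strength) | 728 × 17 = 12,376 | 34 |
| 20 mg | 20 (as written) | 728 × 20 = 14,560 | 40 |
| 20 mg | 10 (tablet strength) | 728 × 10 = 7,280 | 20 |

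Half the period at each dose gives 54 mg/day as written and 27 with tablet strength. The ratio is exactly 2 in every case. With tablet strength, the rule returns the protocol's own doses.

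**3. Can the free-base convention explain it?** No. SAP 11.1 expresses dose levels as free base, and Protocol 5.1.1 equates 10 mg with 11.8 mg of the salt and 17 mg with 20 mg. Those ratios are about 1.18, not 2.

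**4. Would the doubling be visible?** A doubled average exceeds the 34 mg maximum when compliance is above 34/68 = 50% on 34 mg, or above 34/40 = 85% on 20 mg. Below those limits it looks ordinary: on 20 mg at 80% compliance, 0.80 × 40 = 32 instead of 0.80 × 20 = 16 mg/day.

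**5. Double-blind plus open-label (11.1.2).** The open-label part is doubled in the same way. The documents do not give tablets per dose in the antecedent study. As an illustration, assume 56 double-blind days at 34 mg followed by 364 open-label days. With one tablet per dose the literal average is (56 × 34 + 728 × 34)/420 = 63.5 mg/day; with two it is 68. The correct value is 34 in both cases.

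**6. Compliance.** Reported compliance = (taken + lost)/(2 × days). Protocol 5.1.1 says only that kits hold one month's supply, so I assume 28 to 31 days, which is 56 to 62 tablets. One whole unused kit that is lost has this effect:

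| Exposure | Tablets due | Points added | True compliance reported as 80% or more |
|---|---|---|---|
| 364 days | 728 | 56/728 = 7.7 to 62/728 = 8.5 | from 72.3% to 71.5% upward |
| 196 days | 392 | 56/392 = 14.3 to 62/392 = 15.8 | from 65.7% to 64.2% upward |
| 112 days | 224 | 56/224 = 25.0 to 62/224 = 27.7 | from 55.0% to 52.3% upward |

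For example, true compliance of 75% over 52 weeks is reported as 82.7% to 83.5%.

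**The case against.** **The dose rule is only loose wording.** *Dose level* is never formally defined, the multiplier is attached to each kit, and the only salt-to-base equivalence in the protocol is per tablet. A programmer could well use 10 or 17 mg. All subjects start on 34 mg, so a doubled cohort mean would very likely exceed the maximum dose and be noticed in the quality control that SAP 18 describes. This stands as a reason to expect the error to be caught. It does not make the stated rule right, and a validator who programs from the SAP text starts from the same wrong multiplier.

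**The output is not named in 11.1.1.** That section lists no table of average daily dose. This is true; the link to an output rests on Protocol 9.5.3.1 and the general sentence opening SAP 11. SAP 19 declares no departure from the protocol, so the summary is still due.

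**Pill counts are conventional, and Protocol 5.1.6 already covers lost drug.** Dispensed minus returned is a usual convention, and the SAP does not withdraw the testimony rule. Testimony may reach the accountability records in a way the documents do not show. The kit-loss figures assume a whole unused kit, and nothing indicates how often that happens. The 80% limit in Protocol 5.1.6 concerns intervals between visits, whereas the SAP category covers the whole study. All of this stands and keeps the compliance point secondary.

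**Stronger readings.** A reader might infer that reported doses are in fact doubled, that total exposure over both studies is off by exactly two, or that the safety results are compromised. The documents support none of these. They show a rule and no output; they do not give the antecedent study's tablets per dose; and duration, Kaplan-Meier curves, last dose level and adverse event tables do not use tablet counts.

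**Conclusion.** The dose rule in SAP 11.1.1 is wrong as written. Read with the only values the documents give for *dose level*, it doubles open-label cumulative and average daily dose for every subject for whom they are computed. The same holds for the open-label part of 11.1.2; the double-blind part cannot be checked. This needs no assumption beyond reading the term as the documents use it elsewhere.

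The compliance point is real but smaller. As stated, 11.2 counts unreturned tablets as taken, which does not carry through Protocol 5.1.6 and does not match how 11.1.1 handles unreturned kits. Its size, about 8 percentage points over 52 weeks and more with shorter exposure, rests on the assumed kit size and on a whole unused kit being lost, with unknown frequency. It is enough to move some subjects across the 80% category limit.

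Only descriptive dose and compliance summaries are affected. The correction should be made, but no conclusion about the primary endpoint depends on it.

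**What to change.** - **SAP 11.1.1:** state the multiplier as tablet strength (10 mg or 17 mg).
- **SAP 11.1.2:** state it as the strength of the tablets in the kit (mg), which is right whatever the antecedent study supplied.
- **SAP 11.2:** for drug that cannot be returned, use testimony as Protocol 5.1.6 provides. Report the number of subjects with unreturned kits, and either flag those without testimony or show the compliance summary with and without them.

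I would not simply set compliance to missing where there is no testimony. If subjects who fail to return drug also comply less well, which is plausible but not shown, dropping them would flatter the summary.

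The dose correction is a change of phrase in two places plus a check of the program. The compliance change needs a short rule and one extra count or sensitivity display. The documents do not show whether testimony was recorded in usable form; where it was not, those subjects' compliance stays uncertain, but the uncertainty becomes visible.

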11.1.2 Total exposure to double-blind and OL pimavanserin

For subjects who received pimavanserin in the antecedent study, formulas to calculate subject level total pimavanserin (DB+OL) exposure-related quantities are as follows:

$$\text{Total duration of exposure (days)} = (\text{OL last dose date} - \text{OL first dose date} + 1) + (\text{DB last dose date} - \text{DB first dose date} + 1)$$

$$\text{Total average daily dose (mg/day)} = \frac{\text{total cumulative dose (mg)}}{\text{total duration of exposure (days)}}$$

In case a subject whose last dose date in the antecedent study is equal to the first dose date in the OLE, the total duration of exposure will be the above calculation minus one.

The total cumulative dose of pimavanserin will be calculated by first multiplying the number of tablets taken by the dose level (in mg) for each kit returned to the site during both the DB and OL study periods and then summing the results for all kits.

For subjects who received placebo in the antecedent study, the pimavanserin total duration of exposure, total cumulative dose, and the average daily dose across the DB and OL periods will use the same values as calculated for the OL study alone (see Section 11.1.1).

Total duration of DB+OL exposure to pimavanserin will be summarized as both continuous and categorical variables. For the categorical presentation, the number and percentage of subjects in each of the following categories will be displayed: <2 weeks (1 to 13 days), 2 to <4 weeks (14 to 27 days), 4 to <8 weeks (28 to 55 days), 8 to <12 weeks (56 to 83 days), 12 to <16 weeks (84 to 111 days), 16 to <24 weeks (112 to 195 days), 28 to <40 weeks (196 to 279 days), 40 to <52 weeks (280 to 363 days), 52 to <60 (364 to 419 days), and ≥ 60 weeks (≥ 420 days).

In addition, summaries of whether subjects had any dose change (yes vs. no), their highest dose level (20 mg or 34 mg), and their last dose level (20 mg or 34 mg) will also be provided.

11.2 Measurement of Study Drug Compliance

Study drug compliance (in percentage) during the OL study period for a given subject is calculated as follows:

$$\text{Compliance} = \left[\frac{\text{OL tablets dispensed} - \text{OL tablets returned}}{2 \times \text{duration of OL exposure}} \right] \times 100\%$$

Study drug compliance will be summarized descriptively as both continuous and categorical variables. For the categorical presentation, the number and percentage of subjects in each of the following categories will be presented: <80%, 80 to 120%, and >120%.

12 EFFICACY ANALYSES

All efficacy analyses will be performed using the Safety Analysis Set. No hypothesis testing is planned. Descriptive summaries of all efficacy endpoints will be provided.

12.1 Exploratory Efficacy Endpoints

The exploratory endpoints for this study to assess the benefit of pimavanserin are:

- Change from Baseline in CGI-S scale for neuropsychiatric symptoms
- Change from Baseline in SDI score
- Change from Baseline in EQ-5D-5L score

12.2 Adjustment for Covariates

Not applicable.

12.3 Handling of Missing Data

Any derived scores (i.e. total, domain, or subscale scores) that are missing after the imputation of individual missing items as described in [Section 5.3](#) will not be imputed.

12.4 Multiple Comparisons / Multiplicity

No hypothesis testing is planned.

13 METHODS OF EFFICACY ANALYSES

13.1 Analysis of Efficacy Endpoints

Descriptive statistics for all exploratory efficacy endpoints listed in Section 12.1 will be tabulated by cohorts based on antecedent study and DB treatment group at scheduled timepoints. The summaries of the change from Baseline results will be presented by cohort at

scheduled timepoints in two ways as specified in Section 5.2. The scheduled timepoints across the DB and OL study periods for all efficacy endpoints are presented in Table 3 below.

Table 3 Scheduled Assessment Timepoints for Efficacy Endpoints Across ACP-103-046 (DB) and ACP-103-047 (OL)

	CGI-S	SDI	EQ-5D-5L
DB Baseline	x	x	x
DB Week 1	x		
DB Week 2	x		
DB Week 4	x	x	
DB Week 6	x		
DB Week 8/OL Baseline (-046 EOT)	x	x	x
OL Week 2	x		
OL Week 4	x		
OL Week 8	x		
OL Week 12	x	x	x
OL Week 16	x		
OL Week 28	x	x	x
OL Week 40	x		
OL Week 52	x	x	x

13.1.1 EQ-5D-5L

The change from Baseline in the EQ-5D-5L VAS score will be summarized descriptively at each timepoint as described in [Section 13.1](#).

For each EQ-5D-5L dimension the proportion of subjects reporting no, slight, moderate, severe, and extreme/unable to perform activity will be summarized descriptively at each timepoint.

Change from OL Baseline in EQ-5D-5L health state will be assessed with the Pareto classification of health change (PCHC) method. Using this methodology, at each scheduled

timepoint, each EQ-5D health state will be classified into one of four categories, relative to the OL Baseline health state:

- Improved = improved on at least one dimension and not worsened on any other dimension
- Mixed = improved on at least one dimension and worsened on at least one other dimension
- No change = no changes in any dimension
- Worsened = deterioration on at least one dimension and no improvement on any other dimension

If one or more dimensions are missing a valid response, then the PCHC category will not be derived.

The proportion of subjects in each PCHC category will be summarized descriptively at each scheduled timepoint.

The above analyses will also be presented based on the DB cohorts as described in [Section 5.2](#).

14 SAFETY ANALYSES

Safety variables include AEs, TEAEs, clinical laboratory variables, vital signs, body weight, BMI, physical examinations, electrocardiogram (ECG), C-SSRS, GCAS, MMSE, and ESRS-A variables. The safety summaries will be presented for the Safety Analysis Set using descriptive statistics. Safety variables will be summarized by cohorts based on the antecedent study and DB treatment group (see Section 5.2). For each continuous variable in clinical laboratory, vital signs, and electrocardiograms, the change from Baseline will be presented in two ways as specified in Section 5.2.

The scheduled timepoints across the DB and OL study periods for all safety endpoints are presented in [Table 4](#) below.

Table 4 Scheduled Assessment Timepoints for Safety Endpoints Across ACP-103-046 (DB) and ACP-103-047 (OL)

	Vitals	Lab	ECG	MMSE	ESRS-A
DB Baseline	x	x	x	x	x
DB Week 1	x			x	x
DB Week 2	x		x	x	x
DB Week 4	x	x		x	x
DB Week 6	x			x	x
DB Week 8/OL Baseline (-046 EOT)	x	x	x	x	x
OL Week 2	x		x	x	x
OL Week 4	x		x	x	x
OL Week 8	x		x	x	x
OL Week 12	x	x	x	x	x
OL Week 16	x		x	x	x
OL Week 28	x		x	x	x
OL Week 40	x		x	x	x
OL Week 52	x	x	x	x	x

For by-visit summaries, all scheduled and unscheduled values within a visit window will be considered. For the overall post-Baseline summaries, all post-Baseline values will be considered, including unscheduled and out of window values.

14.1 Adverse Events

All AEs, classified by preferred term, will be coded using MedDRA version 23.0 or newer.

An AE (classified by PT) will be considered a TEAE if it started on or after the OL first dose of study drug and no later than the OL last dose date + 30. AEs reported on Day 1 based on pre-dose findings will not be considered as TEAEs.

For the following summaries, the event counts and the number and percentage of subjects reporting TEAEs will be tabulated by cohort and overall:

- TEAEs by SOC and PT
- Most frequently reported TEAEs by SOC and PT
 - PTs reported by $\geq 5\%$ and $\geq 2\%$ (overall) of subjects in the Safety Analysis Set
- TEAEs by PT
- TEAEs by SOC, PT, and maximum severity
 - if more than 1 AE occurs with the same PT for the same subject, the subject will be counted only once for that PT using the most severe occurrence
- TEAEs related to study drug by SOC and PT
- Treatment-emergent serious adverse events (TESAEs) by SOC and PT
- TEAEs leading to discontinuation of study drug by SOC and PT
- AEs with fatal outcome by SOC and PT
- TEAEs with fatal outcome (that occurred within 30 days of last dose) by SOC and PT

For tabulations that include SOC and PT the display will be sorted alphabetically by SOC and then by descending subject frequency for the PTs based on counts in the Safety Analysis Set within each SOC. SOCs will not be included in the TEAEs by PT tabulation. This display will be sorted by descending subject frequency based on counts in the Safety Analysis Set.

An AE listing by subject will display all events, including those which are not TE, and will include the verbatim term in addition to the MedDRA SOC and PT. This listing will also include all relevant eCRF data associated with the event: e.g. date of onset, dose level at date of onset, date resolved, date of the first and last dose of study drug, severity, frequency, outcome, relationship to study drug, action taken with study drug, and required therapy. When a date is presented, the study day associated with the date will also be displayed. Separate listings will be presented for subjects with SAEs, subjects with AEs leading to discontinuation and subjects who died (if any). In these listings, an indicator for TEAEs will also be included.

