6.4 Safety Follow-up

A 30-day safety follow-up telephone call with the subject and study partner/caregiver is to be completed for subjects who complete the study as well as those who discontinue prematurely from the study. Subjects should have the following completed 30 (+4) days after last dose of study drug:

- Assessment of concomitant medications/treatments
- Assessment of AEs

6.5 **Unscheduled Visits**

Unscheduled visits may occur as determined by the Investigator. The following assessments generally should be recorded at each unscheduled visit: assessment of AEs, assessment of concomitant medications/treatments, measurement of vital signs, CGI-S, ESRS-A, C-SSRS (Since Last Visit version) or the GCAS if the C-SSRS cannot be completed. The Investigator may perform any additional safety evaluations deemed to be clinically indicated.

7 **ADVERSE EVENTS**

7.1 **Adverse Events**

Adverse events occurring after the first dose of open-label study drug in ACP-103-047 until safety follow-up assessment (conducted by telephone call) 30 days after the last dose of study drug, will be recorded as an AE in the ACP-103-047 study.

All ongoing AEs from the antecedent study (ACP-103-046) will be carried over and recorded from Baseline for the ACP-103-047 study until resolution or the follow-up safety assessment. All AEs must be either resolved or stable at end of study. If ongoing at the end of the study, the subject should be referred for appropriate treatment.

7.2 **Specification of Safety Parameters**

7.2.1 **Definition of Adverse Event**

An AE is defined as “any untoward medical occurrence associated with the use of a drug in humans, whether or not considered drug related” ([US FDA 2012](#)).

An AE can therefore be any unfavorable and unintended sign (e.g., an abnormal laboratory finding), symptom, or disease temporally associated with the use of a drug, without any judgment about causality or seriousness. An AE can arise from any use of the drug (e.g., off-label use, use in combination with another drug) and from any route of administration, formulation, or dose, including an overdose.

A suspected adverse reaction is any AE for which there is a reasonable possibility that the drug caused the AE.

AEs do not include the following:

- Stable or intermittent chronic conditions (such as myopia requiring eyeglasses) that are present prior to Baseline of the ACP-103-047 study and do not worsen during the study

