9.2 Statistical Hypotheses

No formal testing of hypotheses is planned. All outcomes will be summarized descriptively.

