9.3 Sample Size Determination

Approximately 750 subjects will be enrolled. The sample size for this study is not based on statistical power, but will depend on the number of subjects who transition into this open-label extension study from the antecedent study.

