9.5.1 Primary Analyses

Adverse events will be classified into standard terminology using the Medical Dictionary for Regulatory Activities (MedDRA). All AEs will be listed and summarized by system organ class and preferred term. Summaries by maximum severity will also be provided. Adverse events leading to discontinuation, AEs related to study drug, SAEs, and fatal AEs will also be summarized.

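### The only by-term table of AE-related stopping in SAP 14.1 is limited to TEAEs, so an unworsened AE carried over from ACP-103-046 that ends open-label treatment is listed but not tabulated

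*SAP*

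**What the plan says.** **Definition.** SAP 14.1: "An AE (classified by PT) will be considered a TEAE if it started on or after the OL first dose of study drug". The window closes 30 days after the last open-label dose. The definition rests on onset and does not mention worsening of an existing event.

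**Tabulation.** Among the planned AE tables in SAP 14.1, the one on stopping is "TEAEs leading to discontinuation of study drug by SOC and PT". SAP 14.1.1 repeats the same set of tables by relationship to COVID-19. For deaths, SAP 14.1 plans both an all-AE table and a TEAE table.

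**Carried-over events.** Protocol 7.1: "All ongoing AEs from the antecedent study (ACP-103-046) will be carried over and recorded from Baseline for the ACP-103-047 study". They stay on record until they resolve or until the follow-up assessment.

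**Protocol commitment.** Protocol 9.5.1: "Adverse events leading to discontinuation, AEs related to study drug, SAEs, and fatal AEs will also be summarized". That section sets no treatment-emergent limit. SAP 19 reports no changes to the protocol's analyses.

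**Other outputs.** SAP 14.1 plans a separate listing of subjects with AEs leading to discontinuation. It is not confined to TEAEs and carries a TEAE indicator. SAP 6 counts discontinuations from the study by reason, and Protocol 4.4 includes adverse event among the reasons.

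**The concern.** In a parallel-group trial, an AE that is not treatment-emergent normally began before the study drug. In a rollover study that no longer follows. Cohort 2 took pimavanserin during ACP-103-046, so an AE ongoing at rollover may have begun on the drug and may later be the reason for stopping it. An onset rule anchored to the first open-label dose classes that AE as not treatment-emergent, and the only table of stopping by term leaves it out.

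The antecedent study will not normally show it as a stopping event either. Inclusion criterion 3 requires that the subject completed that study or was in one that the sponsor ended early, so the stopping happens in ACP-103-047. The primary objective is long-term safety and tolerability, and the terms for which subjects give up treatment are a central part of tolerability. At stake is whether that summary is complete, and whether it matches what the protocol said would be summarized.

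**Working it through.** The plan states no figure on this point, and "No formal testing of hypotheses is planned", so there is no power or alpha calculation to reproduce. The check follows one event through the rules.

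**Trace of a carried-over AE with known onset and unchanged grade**

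1. *Is it in the ACP-103-047 data?* Yes, under Protocol 7.1.
2. *When did it start relative to open-label dosing?* Before it. The event is ongoing at the Baseline visit, and Protocol 5.1.3 puts the first dose on the following day.
3. *Is it re-dated?* Only if it worsens. Protocol 7.3.2.1 gives a new start date to a marked and lasting worsening in severity. An event that persists at the same grade keeps its double-blind onset date.
4. *Does the missing-date rule bring it in?* No. SAP 5.5.3 defaults to treatment-emergent only when the order of onset is unclear from the dates. Here the onset is known.
5. *Is it a TEAE?* No, by the SAP 14.1 onset rule.
6. *Where does it appear if the subject stops open-label drug because of it?*

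| Planned output | Shows the event? | Shows SOC/PT? | Counts and percentages? |
|---|---|---|---|
| TEAE discontinuation table (SAP 14.1) | No | – | – |
| COVID-19 split of that table (SAP 14.1.1) | No | – | – |
| Listing of AEs leading to discontinuation (SAP 14.1) | Yes, flagged as not TE | Terms available through the all-AE listing | No |
| Disposition by reason (SAP 6) | Subject counted if the reason is adverse event | No | Yes, named by region and overall |

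The event is therefore reported, but no summary by term includes it.

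**Protocol against SAP.** Protocol 9.5.1 speaks of adverse events leading to discontinuation. SAP 14.1 tabulates TEAEs leading to discontinuation, a subset, and SAP 19 lists no change.

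**Size (assumptions only).** The documents give no rate of carried-over AEs or of stopping because of them. Let c be the percentage of subjects who stop for such an AE.

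- Planned enrolment: "Approximately 750 subjects will be enrolled". With c = 0.5%, 0.005 × 750 = 3.75. With c = 2%, 0.02 × 750 = 15. That is about 4 to 15 subjects.
- SAP 16.1 counts 353 rollovers at the second interim analysis. On that number, 0.005 × 353 = 1.8 and 0.02 × 353 = 7.1, or about 2 to 7 subjects.
- If TEAE discontinuations affect t% of subjects, and these are different subjects, the share of AE-related stopping missing from the table is c/(t + c). For c = 1 and t from 15 down to 5, this is 1/16 = 6% to 1/6 = 17%. For c = 0.5 it is 0.5/15.5 = 3% to 0.5/5.5 = 9%.

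Both c and t are assumed. The figures show only how the gap would scale.

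**The case against.** The strongest reply is that nothing is lost. The listing identifies every AE that led to stopping and marks whether it was treatment-emergent, and disposition counts the subject. The primary endpoint in both documents is TEAEs, and restricting tables to TEAEs is common practice. On that view the SAP implements Protocol 9.5.1 and does not depart from it. The affected group is also narrow. Exclusion criterion 1 can remove subjects judged unsuitable because of AEs in the antecedent study, worsened events are re-dated, and unclear onset counts as treatment-emergent. Most of this stands. What remains is that a listing gives no counts, percentages or cohort display, and that the protocol promised a summary without the TEAE limit.

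A reader might infer more than the documents support:

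- *The events are hidden or fall between the two studies.* They are absent from one table only. The listing shows them.
- *They are drug-caused tolerability failures in Cohort 2.* Protocol 7.1 carries over every ongoing AE. Some may predate double-blind dosing, and causality is a separate judgment.
- *The cohort comparison is distorted.* Both cohorts lose such events, the net direction is unknown, and the display is descriptive.
- *Disposition will fail to reconcile because of this.* SAP 6 counts stopping the study and SAP 14.1 counts stopping the drug. Exact agreement is not guaranteed in any case.
- *The SAP already solved the problem for deaths.* Its pair of fatal-event tables is distinguished by timing after the last dose. It shows that a paired display is acceptable in this SAP, but not that it was designed for carried-over events.
- *A table of SAEs by when they became serious is equally easy.* Protocol 7.3.2.6 records serious or not serious. The documents do not show that the date on which seriousness was reached is collected.

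**Conclusion.** The gap is real but narrow. A carried-over AE with known onset and no re-dated worsening that ends open-label treatment is missing from the only table of AE-related stopping by term. That table is narrower than the protocol's wording, and SAP 19 does not say so. The event remains visible in the listing and, without a term, in disposition.

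The logic is certain on the text, provided sites re-record a marked worsening as Protocol 7.3.2.1 describes. If they do not, the gap would be wider, because the TEAE definition has no worsening clause of its own. The number of cases is not in the documents and is probably small. The 4 to 15 subjects in 750 rest on an assumed 0.5% to 2%. This is a low-cost improvement to the completeness of the tolerability summary. It is not evidence that the plan conceals safety findings.

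**What to change.** In SAP 14.1, beside the existing TEAE table, add a table by SOC and PT of **all** AEs that led to stopping open-label drug, by cohort and overall, with carried-over events flagged or shown as a sub-row. Add a short note explaining any difference from the number discontinued for adverse event in the disposition table. It would also help to state in the TEAE definition how a worsening of a carried-over AE is handled. If the extra table is not wanted, the restriction to TEAEs should at least be declared in SAP 19.

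If a serious-event counterpart is wanted, tabulate all SAEs recorded in ACP-103-047 with a TE flag, in line with Protocol 9.5.1. Do not base it on the date a seriousness criterion was met.

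The cost is one additional table and a few lines of SAP text. Action taken with study drug is already recorded for each AE (Protocol 7.3.2.3), so no new data are needed and study conduct does not change. The downside is that the reported figure for AE-related stopping may rise slightly. In Cohort 1 the added rows would include events that began on placebo, which is why the flag is needed.
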